2.2 Study Population

The study population consists of patients with diagnosed COPD who are registered at general practices providing data to OPCR and who have at least one blood eosinophil count available. For objectives 2, 3 and 4 patients from CPRD who have linkage to HES will be selected.

2.3 Inclusion Criteria

Overall inclusion criteria:

1. A diagnostic Read code for COPD³ qualifying for inclusion in the register of patients with COPD recorded after 1st April 2008 (21)
2. Age \geq 40 years at the most recent diagnostic code and at index dates
3. \geq 1 valid blood eosinophil count measured when there was no recent exacerbation recorded, i.e., within 4 weeks prior to or at the measurement
4. Valid continuous data in a baseline year prior to index date
5. At least one year of continuous outcome data after the index date, except for patients included in the study of objective 2, in which patients lost to follow up are censored

Objective-specific inclusion criteria:

6. Objective 1:
Stable COPD therapy, i.e. no change in treatment regimen, ICS dosage and substance during baseline and outcome years
7. Objective 2:
 - a. Hospital discharge of admission with COPD exacerbation as diagnosis
 - b. Blood eosinophil count measured at the time of no recent exacerbation within 1 year prior to ID
8. Objectives 2, 3 and 4:
Linkage to HES data available

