2.5 Study designs

2.5.1 Objective 1

The index date (ID) of objective 1 will be the most recent date of a recorded blood eosinophil count, measured at the time of stable disease, defined as no COPD exacerbation within 4 weeks prior to or at ID and no change in treatment regimen, ICS dosage and substance during the study period (Figure 1).

[figure not shown]

Figure 2. Study design objective 1

Patient's demographics and clinical characteristics will be described and potential confounders will be assessed in a baseline year prior to ID.

The association between high blood eosinophil counts (at ID) and (moderate or severe) COPD exacerbations in the subsequent year will be assessed in subgroups of patients defined by smoking status (active smoker in baseline year or not) and the following treatments in the baseline year (22):

1. Short-acting bronchodilators as required only (SABA and/or SAMA)
2. Maintenance therapy with LAMA and/or LABA
3. ICS / LABA in combination inhaler
4. Triple therapy: ICS + LABA + LAMA

The primary definition of "high eosinophil counts" will be $\geq 0.45 \times 10^9/L$, based on our previous work. Sensitivity analyses will be performed using 0.25, 0.35 and 0.55 as cut-points.

Sensitivity analyses will be performed in the subgroup of patients with COPD who have never been diagnosed with asthma, i.e., no diagnostic Read code for asthma recorded ever.

Additional analyses will be performed to evaluate whether the Medication Possession Ratio (MPR) for maintenance treatments (ICS / LAMA / LABA) modifies the associations by:

1. Including interaction terms of blood eosinophil counts and MPR into the regression model (continuous or categorical depending on best model fit) to explore whether MPR significantly modifies the association and at which values
2. Repeating analyses in patients with good adherence to ICS, using the widely used cut-point of $MPR \geq 80\%$ for therapy options 3 and 4

2.5.2 Objective 2

The ID of objective 2 will be the date of the most recent first discharge from hospital admission for COPD exacerbation occurring within one year after a blood eosinophil count measured at the time of no recent exacerbation (Figure 3). Patients will be followed after ID until re-admission or death to a maximum of one year after each index date.

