3. VARIABLES AND EPIDEMIOLOGICAL MEASUREMENTS

3.1 Determinants of COPD exacerbations

3.1.1 Definition of high blood eosinophil counts

Only eosinophil counts measured at the time of stable COPD will be eligible for selection at the most recent measurement. Stable COPD is defined as absence of a recorded COPD exacerbation within 4 weeks prior to or at the eosinophil count recording date, as our previous work showed that eosinophil counts were relevantly decreased within patients when oral corticosteroids courses were prescribed within 4 weeks prior to ID and when antibiotics were prescribed at ID.

The primary definition of high blood eosinophil counts will be $\geq 0.45 \times 10^9/L$, based on previous work. Sensitivity analyses will be performed using ≥ 0.25 , $\geq 0.35 \times 10^9/L$ and $\geq 0.55 \times 10^9/L$ as cut-points.

A sensitivity analysis adjusted for the neutrophil count / neutrophil-to-lymphocyte ratio as markers of infection (23) will be performed in patients who have these measurements available.

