3.1.2 Treatment regimens

For objective 1, groups of patients using the following treatment regimens are analysed:

1. Short-acting bronchodilators as required only (SABA and/or SAMA)
2. Maintenance therapy with LAMA and/or LABA
3. ICS / LABA in combination inhaler
4. Triple therapy: ICS + LABA + LAMA

Treatment category will be assessed based on ≥ 1 prescriptions in the baseline year.

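### The COPD code need not precede the index date, so patients undiagnosed at index can enter the objective 3B comparator and objective 4

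*Protocol*

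**What the plan says.** Protocol section 2.3 sets the eligibility rules for all objectives.

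- Criterion 1 requires a COPD Read code "qualifying for inclusion in the register of patients with COPD recorded after 1st April 2008".
- Criterion 2 requires age 40 or over, in "years at the most recent diagnostic code and at index dates". It treats the code and the index as separate dates and does not order them.
- Criterion 4 asks for "Valid continuous data in a baseline year prior to index date".
- Criterion 5 asks for "At least one year of continuous outcome data after the index date", with an exception for objective 2.

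Section 2.5.1 states that the objective 1 index date "will be the most recent date of a recorded blood eosinophil count, measured at the time of stable disease". Sections 2.5.3 and 2.5.4 use the most recent count taken with no recent exacerbation. Section 3.1.1 then gives the meaning of stability: "Stable COPD is defined as absence of a recorded COPD exacerbation within 4 weeks prior to or at the eosinophil count recording date".

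Section 2.2 describes the population as people with a COPD diagnosis and gives no date for it. By contrast, section 3.3.1 requires comorbidity codes to be recorded before the index date and smoking status to come from the five years before it.

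**The concern.** The condition that defines the cohort is the one characteristic with no time anchor to the index date. A person not yet diagnosed passes the stability test, because that test asks only that no exacerbation was recorded in the four weeks up to the count. Applied literally, the rules allow part or all of the baseline and outcome years to lie before the qualifying COPD code.

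Such a patient is in the cohort because of information that arose after the index date. Before diagnosis the patient would be expected to generate fewer COPD-coded consultations and admissions. If these patients sit in the total COPD population that serves as denominator in objective 3B, but hardly at all in the triple-therapy subgroups that serve as numerators, the cost ratios move upward. That is the direction of the hypothesis in section 1.3, which expects high costs in the triple-therapy, high-eosinophil group. In objective 4, baseline treatment, exacerbation count and missing FEV₁ are candidate predictors. They could partly indicate who was already diagnosed, as well as what drives cost in COPD.

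**Working it through.** The protocol gives no figure on this point, so there is none to reproduce. The check has three parts.

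**1. How far each objective is exposed**

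- *Objective 1: narrowed, not closed.* Section 2.3 requires "Stable COPD therapy, i.e. no change in treatment regimen, ICS dosage and substance during baseline and outcome years", which removes many undiagnosed patients. But section 3.1.2 assigns a treatment group on one or more "prescriptions in the baseline year", and section 2.4 keeps patients with asthma, so an inhaler before the index date does not prove COPD by then. The classical COPD subpopulation of section 3.4.1 is better protected: it needs airflow obstruction recorded before the index date and no asthma diagnosis.
- *Objective 2: largely closed.* The index is discharge from an admission coded J44.0 or J44.1, so COPD is in the hospital record by then, even if the Read code follows later.
- *Objective 3A: narrowed.* The four subgroups need triple therapy plus an exacerbation history in the baseline year.
- *Objective 3B comparator and objective 4: open.* Neither has a treatment or exacerbation requirement.

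**2. Possible size in objective 3B**

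Inputs, all assumptions: f is the share of the comparator undiagnosed at index (5% to 12%). q is their mean COPD-related cost as a fraction of the mean D in diagnosed patients (0 to 0.5). The subgroup mean S is taken as unaffected.

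Comparator mean = D × [(1 − f) + f × q] = D × [1 − f(1 − q)]

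Observed ratio = S / (D × [1 − f(1 − q)]), so the inflation factor is 1 / [1 − f(1 − q)].

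- f = 0.05, q = 0.5: 1/0.975 = 1.026
- f = 0.05, q = 0: 1/0.95 = 1.053
- f = 0.12, q = 0.5: 1/0.94 = 1.064
- f = 0.12, q = 0: 1/0.88 = 1.136

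The range is about 3% to 14%. The upper value of f is the share of first codes falling in one year if they were spread evenly from April 2008 to late 2016, about 8.6 years (1/8.6 = 11.6%). The protocol states no data end, and this is not an estimate of the cohort share.

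The inflation applies to each subgroup against the total population. It cancels when one subgroup ratio is divided by another, because both share the denominator: (S₁/T)/(S₂/T) = S₁/S₂.

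**3. Possible size in objective 1**

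Assume the undiagnosed share f is the same in both eosinophil groups, the rate ratio among the undiagnosed is 1, and q is now their exacerbation rate relative to diagnosed patients (0.5 to 1).

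Observed RR = [(1 − f) × 1.3 + f × q] / [(1 − f) + f × q]

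- f = 5%: 1.29 (q = 0.5) to 1.285 (q = 1)
- f = 10%: 1.28 to 1.27
- f = 20%: 1.27 to 1.24

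Scaling the protocol's 1,645 patients per treatment group by (ln 1.3 / ln observed RR)² gives about 1,720 at the mildest setting and 2,450 at the most severe. Section 3.6.1 expects 5,000 to 8,000 per group, of whom 3,400 to 5,500 are not active smokers. The issue in objective 1 is who is being described, not sample size.

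**The case against.** The strongest reply is that the intent is plain: section 2.2 speaks of diagnosed patients, section 3.1.1 of stable COPD, and the design diagrams (Figures 2 to 5, not available for this point) may show diagnosis before index. The intent is probably right, but an extraction follows the written criteria, and these would accept a later code.

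Three stronger readings are tempting and are not supported.

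- *A reader might infer that about 12% of the cohort must enter before diagnosis.* The 11.6% is a share of first codes under an assumed data end. Criterion 1 asks for a code after April 2008, not a first code, so patients with long-standing COPD also qualify and lower the share. Entry is not unavoidable either: a patient first coded in the last data year whose most recent count also falls in that year fails criterion 5. Such a patient enters only if an older count is taken instead, which the protocol does not say.
- *A reader might infer that these patients have no COPD-related cost.* Anyone coded during the outcome year has some COPD-coded care. Sections 3.2.4 and 3.2.5 also count inhalers, oral steroids, antibiotics with a lower respiratory consultation, and attendances for other lower respiratory conditions, none of which needs a COPD code. Lower cost is probable; zero is only the limiting case.
- *A reader might infer that the high-versus-normal eosinophil contrast in objective 4 is biased.* Nothing in the protocol shows that undiagnosed patients are distributed differently by eosinophil count, and baseline exacerbations, FEV₁, MRC score and treatment are candidate predictors that partly separate them.

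What remains after these concessions is the unordered criterion and its effect on the 3B denominator and on the population described in objective 4.

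**Conclusion.** The point holds in a limited form. As written, a patient whose index count predates the COPD code can enter. How many do is unknown. Objective 2 is largely protected, objective 1 and the 3A subgroups are partly protected, and the 3B comparator and objective 4 are unprotected.

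For 3B the probable effect is an upward shift in the COPD-related cost ratios, of about 3% to 14% under the stated assumptions (5% to 12% undiagnosed at index, at 0% to 50% of the average cost, numerators unaffected). The documents support no narrower range. For all-cause cost ratios they do not settle the direction. For objective 4 the consequence is a cohort that partly does not have diagnosed COPD at the time its predictors are measured; its size cannot be stated.

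**What to change.** Amend criterion 1 so that the qualifying COPD Read code, the one dated after 1 April 2008, must be recorded on or before the index date. Apply it to all objectives and repeat it explicitly for the total population in objective 3B and for objective 4. Name the qualifying code: a rule on the first COPD code of any date would let through a patient with an older code whose qualifying code comes after the index date.

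Requiring the code before the start of the baseline year would also drop newly diagnosed patients and so change the target population. That stricter rule is better kept as a sensitivity analysis.

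The cost is one clause, made before data extraction, and a modest loss of patients, mainly from the comparator and sub-study 4.

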To date, guidelines mention that no treatment has been shown to influence the accelerated decline in lung function that is characteristic of COPD, highlighting the limited treatment options for this patient population (12). Post-hoc analyses of trial data suggest that patients with high blood eosinophil counts may benefit from inhaled corticosteroids (ICS) treatment in terms of a lower rate of decline in FEV₁ (13), but this requires confirmation in specifically designed studies. Both NICE and GOLD strategy documents recommend the use of ICS as part of a fixed dose combination (FDC) ICS/LABA treatment for patients who have 2 or more exacerbations per year or moderate to severe airflow limitation (FEV₁ <50% predicted normal) (GOLD groups C and D) (Figure 1). Most ICS/LABA combinations are indicated for symptomatic treatment of patients with COPD with FEV₁ $\leq 70\%$ predicted.

However, there is an increasing body of evidence suggesting a link between treatment with

high doses of ICS and the risk of comorbidities, such as cataracts, osteoporosis and pneumonia events, clearly associated with systemic/oral corticosteroids (14-17).

Despite these guidelines, real-world studies indicate that pharmacological treatments often differ from the recommendations. ICS is frequently prescribed to patients with less severe COPD (2). This may reflect the heterogeneity of COPD with different treatment effects of ICS in different subgroups of patients with COPD.

Algorithm showing use of inhaled therapies.

John O'Reilly, and Michael Rudolf Thorax 2011;66:93-96

Figure 1. COPD Therapy guidelines by NICE (16).

COPD is associated with high mortality and morbidity. Hospitalizations for acute exacerbations of COPD account for a relatively large proportion of annual direct costs for COPD (3). Furthermore, one in five patients is estimated to require re-hospitalization within 30 days of discharge after an admission for acute exacerbation, indicating a lack of effectiveness of standard treatment to prevent future exacerbations in a substantial proportion of COPD patients (3). A recent study found that patients with relatively low blood eosinophil counts ($\leq 2\%$) and high CRP levels measured at exacerbation had higher re-admission rates during 6 months of follow up than eosinophilic patients (18). However, low blood eosinophil

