1.2 Rationale

Previous work conducted at OPRI found an increased risk of exacerbations with high blood eosinophil counts. However, the role of different treatment regimens in the association between blood eosinophil count and COPD exacerbations needs to be further elucidated. It is unknown whether the association is also present in the subgroup of patients with COPD who are adherent to ICS and in patients on triple therapy, to which one third of UK patients with COPD progresses in real life (2).

It is also unknown whether patients who have high blood eosinophil counts at the time of stable disease and who experience an exacerbation that requires hospitalization have an increased risk of short-term recurrence of exacerbations and re-admission to hospital.

To our knowledge there is no information available on the burden and cost of COPD in patients on triple therapy who have high blood eosinophil counts and experience frequent exacerbations.

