3.2 Outcomes

3.2.1 COPD exacerbations

The primary outcome for sub-study 1 will be the number of COPD exacerbations in the outcome period, defined as the occurrence of one or more of the following events:

- a. Respiratory-related hospital attendance / admission AND/OR
- b. Respiratory-related A&E attendance AND/OR
- c. An acute oral corticosteroid course AND/OR
- d. Antibiotics prescribed with evidence of a lower respiratory consultation

Where ≥ 1 of these events occur within 2 weeks of each other, they will be considered to be the result of the same exacerbation (and will only be counted once).

The number of acute oral corticosteroids courses will be analysed as secondary outcome for sub-study 1.

A sensitivity analysis will be performed with a more specific (but less sensitive definition) of acute oral corticosteroids courses with evidence of a lower respiratory consultation (Read code for lower respiratory consultation with prescription).

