3.6 Sample Size and Power Calculations

3.6.1 Sub-study 1

Figure 6 shows that 1,645 patients are required for each therapy group to find a significant ($\alpha=0.05$) Rate Ratio of 1.3 as previously found with 80% power, when analysing the association between high blood eosinophil counts and the number of exacerbations, assuming 10% of patients having high blood eosinophil counts and mean rate of events of 0.68 in patients without high blood eosinophil counts as previously observed.

Table 2 shows the proportions of COPD patients on different treatment options in a previous study of OPCRD patients with COPD.

Table 2. Frequencies of therapy options in a previous OPCRD study of patients with classical COPD

Therapy option	Frequency (%) in classical COPD patients
SABA and/or SAMA	18
LAMA and / or LABA	11
ICS / LABA combined	17
Triple therapy	14

Around 46,000 COPD patients from OPCRD are estimated to be available for analyses of whom one third is expected to be an active smoker. Thus, 5,000 to 8,000 OPCRD patients are estimated to be available for each treatment group of whom 3,400 to 5,500 are not active smokers.

[figure not shown]

Figure 6. Total sample size (Y-axis) required for finding different Rate Ratio's (X-axis) significant with 80% statistical power, assuming a mean rate of events of 0.68 in patients without high blood eosinophil counts and a prevalence of 10% of high blood eosinophil counts

3.6.2 Sub-study 2

A recent study performed in Scotland found hospital admission rates of 127 per 1,000 patient years for COPD exacerbations at any diagnostic position (24). In that study, 10% of re-admission occurred within 14 days.

Around 10,000 patients with a blood eosinophil count available within one year prior to a hospital admission for COPD recorded in HES are required for finding a hazard ratio of 1.3 significant ($\alpha=0.05$), assuming a baseline re-admission risk of 10% and 10% of patients having high blood eosinophils (Table 3).

Table 3. Numbers needed for finding different Hazard Ratio's

Hazard Ratio high vs normal	Re-admission risk in patients with normal eosinophil counts	Prevalence of high eosinophil count	Total number of COPD patients required	Numbers needed normal / high	Power at $\alpha=0.05$
1.4	10%	10%	5,729	5,161 / 568	80%
1.3	10%	10%	10,079	9,080 / 999	80%
1.2	10%	10%	22,442	20,218 / 2224	80%

3.6.3 Sub-study 3

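### Objective 1 requires unchanged therapy through the outcome year, so patients can be removed because of the exacerbations being counted; the resulting bias in the eosinophil rate ratio has unknown size and direction

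*Protocol*

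**What the plan says.** Section 2.3, item 6 makes eligibility for objective 1 conditional on "Stable COPD therapy, i.e. no change in treatment regimen, ICS dosage and substance during baseline and outcome years". Section 2.5.1 repeats the condition within its definition of stable disease: "no change in treatment regimen, ICS dosage and substance during the study period". The wording of objective 1 (synopsis and section 1.4) and the synopsis paragraph on the study population carry the same requirement.

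The outcome is measured in the same window. Section 3.2.1 states: "The primary outcome for sub-study 1 will be the number of COPD exacerbations in the outcome period".

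The regimen groups do not need the outcome year. Section 3.1.2 assigns them from one or more "prescriptions in the baseline year", and 2.5.1 likewise refers to baseline-year treatment.

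The protocol also supplies the link from exacerbation to therapy change. Section 1.1 reports that guidance recommends "ICS/LABA treatment for patients who have 2 or more exacerbations per year", among other indications. Section 1.2 describes triple therapy as the regimen "to which one third of UK patients with COPD progresses in real life".

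**The concern.** The question is framed prospectively: given a stable-state eosinophil count, how many exacerbations follow in the next year? At the index date nobody knows who will stay on the same regimen, dose and substance for twelve more months. A patient who exacerbates and is then escalated drops out of the cohort altogether, together with the exacerbations that led to the change. A comparable patient who does not exacerbate has one reason fewer to be removed. This is selection on a consequence of the primary outcome.

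Two results are at stake. The first is the exacerbation rate in each regimen group. The second is the rate ratio for high against normal eosinophils. Room to escalate differs between, say, short-acting bronchodilators only and triple therapy, so the distortion need not be the same in each group. A difference in rate ratios between regimens could then partly reflect the selection.

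Nothing planned would reveal this. The sensitivity analyses vary the eosinophil cut-point, asthma status, the steroid-course outcome definition, adjustment for neutrophil measures and the handling of missing covariates. None relaxes the outcome-year condition or censors at therapy change. Section 3.5.1 offers confounder adjustment, which does not undo selection on the outcome, and the limitations in 3.5.2 do not mention it.

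**Working it through.** **Inputs from the protocol (3.6.1 and 3.4.1).** Reference rate 0.68 in the one-year outcome period; 10% with high eosinophils; "Rate Ratio of 1.3 as previously found with 80% power"; alpha 0.05; negative binomial analysis. The rate with high eosinophils is therefore 0.68 × 1.3 = 0.884.

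**The plan's own figure.** A square-root Poisson formula with two-sided alpha gives

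N = (1.960 + 0.842)² × (1/0.1 + 1/0.9) / [4 × (√0.884 − √0.68)²] = 1,632,

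against the stated 1,645 (0.8% apart). The sample-size arithmetic is not at fault.

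**Inputs the protocol does not give (assumed).** The negative binomial dispersion k, and the probability c that one outcome-year exacerbation leads to a therapy change and hence removal. I use k = 1 as the central value with a range of 0.5 to 2, and c from 10% to 30%.

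**Model.** A patient with Y exacerbations is kept with probability (1 − c)^Y. Negative binomial counts weighted in this way stay negative binomial, with

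- retained mean = (1 − c)μ / (1 + ckμ)
- share retained = (1 + ckμ)^(−1/k)

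**Worked case, k = 1, c = 20% in both groups.**

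- Normal: 0.8 × 0.68 / (1 + 0.2 × 0.68) = 0.544 / 1.136 = 0.479; removed 1 − 1/1.136 = 12%.
- High: 0.8 × 0.884 / (1 + 0.2 × 0.884) = 0.7072 / 1.1768 = 0.601; removed 1 − 1/1.1768 = 15%.
- Ratio: 0.601 / 0.479 = 1.255.

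**Scenarios, k = 1.**

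| c normal | c high | rate normal | rate high | rate ratio |
|---|---|---|---|---|
| 0 | 0 | 0.680 | 0.884 | 1.30 |
| 10% | 10% | 0.573 | 0.731 | 1.276 |
| 20% | 20% | 0.479 | 0.601 | 1.255 |
| 30% | 30% | 0.395 | 0.489 | 1.237 |
| 20% | 30% | 0.479 | 0.489 | 1.02 |
| 30% | 20% | 0.395 | 0.601 | 1.52 |

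With equal c of 10-30% the reference rate is 16% to 42% too low (1 − 0.573/0.68 and 1 − 0.395/0.68), while the ratio moves only from 1.30 to 1.28-1.24.

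**Sensitivity to k (0.5 to 2).** Equal c of 10-30%: reference rate 0.34-0.59, ratio 1.20-1.29. Unequal, 20% normal and 30% high: 0.95-1.07. Reversed, 30% and 20%: 1.50-1.55. In the limiting Poisson case (k = 0) with equal c, both rates shrink by the factor 1 − c and the ratio stays at 1.30.

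**A trigger closer to the guideline.** Suppose only patients with two or more exacerbations can be removed, and a share s of them is (k = 1, equal in both groups). In the normal group P(Y = 1) = 0.241, P(Y ≥ 2) = 0.164, and patients with Y ≥ 2 contribute 0.68 − 0.241 = 0.439 to the mean. The retained rate is (0.241 + (1 − s) × 0.439) / (1 − s × 0.164): 0.61 at s = 20% and 0.50 at s = 50%. The same steps with mean 0.884 give ratios of 1.29 and 1.27.

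**The case against.** The restriction is deliberate. Objective 1 itself includes stable treatment over the study period in its notion of stable COPD, presumably so that the association is seen with the regimen held constant. Conditioning on the baseline year alone answers a somewhat different question, and if ICS acts differently by eosinophil level, time after a step-up mixes regimens. This stands, and it is a reason to keep the restricted set as a labelled analysis. It does not make the restricted set a sound basis for a prospective rate, because that set is defined by events after the index date.

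The trigger model is also simple. The criterion removes any change, including step-downs and product switches, so patients without exacerbations can be removed too; if step-downs are commoner among them, the loss in the rates is partly offset. Section 1.1 notes that real-world prescribing often departs from guidance. These points make the size uncertain but leave the mechanism in place.

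Three stronger readings are tempting, and the documents support none of them.

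- A reader might infer that the ratio is pulled toward or past the null. That holds for equal probabilities with overdispersion (toward only) or for more frequent changes with high eosinophils; the reverse inflates the ratio to about 1.5.
- A reader might infer large attenuation from eosinophil-guided prescribing, for example 20% against 40%, which gives 0.82. The background says that eosinophils may help identify patients who benefit from ICS; it does not say that practices in this database prescribed by the count. Nothing supports such a doubling.
- A reader might infer that rates are materially understated in every regimen. Patients already on triple therapy have little left to escalate to, so the effect there may be small. The protocol also plans analyses within regimens and no formal contrast between them.

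**Conclusion.** The concern holds as a design flaw in the primary analysis of sub-study 1. Following the plan exactly makes eligibility depend on a possible consequence of the outcome, and no planned analysis or stated limitation addresses it. Retained rates are too low wherever exacerbations prompt therapy changes, by an amount that probably differs by regimen.

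For the rate ratio, which is the main target, neither size nor direction can be settled from the protocol. If the chance of a change per exacerbation is the same in both eosinophil groups, the bias is modest: 1.28-1.24 instead of 1.30 at dispersion 1. If that chance differs by ten percentage points, the ratio could be near 1.0 or near 1.5. All these figures rest on an assumed dispersion, assumed change probabilities and a constant chance of removal per exacerbation. They are scenarios, not estimates of the bias in these data.

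**What to change.** In 2.3 (item 6), 2.5.1, section 1.4 and the matching synopsis wording (objective 1 and study population), require no change in regimen, ICS dosage and substance during the baseline year up to the index date only. All of these places must change together, or the criteria will contradict the objective. Analyse patients by baseline regimen and count all exacerbations in the outcome year.

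Keep the stable-in-both-years set as a labelled sensitivity analysis. If the sponsor wants a constant-regimen estimate, censor at the first therapy change, use a log person-time offset, and count the exacerbation that triggered the change. Report how many patients the outcome-year condition removes, by eosinophil group and regimen, and list the selection in 3.5.2 as a limitation of the restricted set.

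The cost is a wording change and an extra analysis run on data already held; the sample grows. The downside is small: some outcome time falls after a therapy change, so the estimate refers to the regimen at index and not to continued use of it.
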